25. LOCAL NUMBER OF SUBJECTS

Phase 1 Aim 1 (Develop OARSCM): 30 individuals with OUD and 30 providers/clinicians will be recruited to provide feedback to improve the interface and features.

Phase 2 Aims 1 & 2 (RCT of OARSCM): 102 patients will be enrolled and randomized into OARS+CM (n=51), or TAU with MyMAT (n=51) to determine efficacy of OARSCM. See grant: "RESEARCH STRATEGY" (p12) "Procedures" for further details.

26. CONFIDENTIALITY

Potential risks due to loss of confidentiality will be minimized by having all information collected and handled by research staff and Q2i employees trained to deal appropriately with sensitive clinical issues. All research personnel and Q2i employees will receive training in research ethics. All information will be treated as confidential material and will be available only to research and clinical staff, including Q2i employees working on the project. All paper-based materials, like consent forms, will be kept in locked files. All datasets will be handled in a HIPAA compliant manner, will be password protected, and the analytic dataset hosted by UMMS will be de-identified after the study is completed, data is cleaned, and primary analyses are completed. After primary analyses are completed, de-identified data will be kept by Q2i for mobile application improvement, such as predictive analytics. For additional information on processes to mitigate loss of confidentiality, please see grant "HUMAN PARTICIPANTS PROTECTION" (p.19-20) "Protection Against Risk."

Certificate of Confidentiality: As of October 1, 2017, all NIH funded research collecting or using identifiable, sensitive information will automatically be issued a certificate of confidentiality (aka applications are no longer needed). The NIH is no longer doing physical certificates, but rather the Notice of Award and Grants Policy Statement will suffice as documentation of CoC protection. See link below for the full policy details. https://grants.nih.gov/grants/guide/notice-files/NOT-OD-17-109.html

Audio recordings: Audio recordings of all interviews will be obtained, unless the participant declines. The sound files will be recorded on digital voice recorders then downloaded to a password protected folder on a secure drive hosted by UMass. After downloading to the secured drive, the recordings will be erased from the voice recorders. All data will be transcribed and stored electronically on password-protected laboratory computers and in REDCap. Audio recordings will be destroyed 5 years after the study ends.

27. Provisions to Protect the Privacy Interests of Subjects

The following security protocols will be applied to all data: physical protections - all databases and systems will be hosted behind the firewall by UMass Medical School and employ user authentication and role-based security for access. Standard security access procedures designed by UMass Medical School will be used to ensure that only authorized research staff has access to the study data. All paper-based materials, like consent forms, will be kept in locked files; logical protections - All datasets will be handled in a HIPAA compliant manner, will be password protected, and the analytic dataset will be de-identified – All urine samples will be stored in locked medical storage containers per the MAT clinic's policy. Results of tox screens from the urine samples are secondary data for this study and urine samples will not be kept by the study team.

OARSCM and MyMAT: The OARSCM and MyMAT applications reside on a secure server maintained by Q2i. All transmissions are encrypted for security. No data is stored outside of Q2i's secured, encrypted, AWS environment. DATA at rest: AES – 256 encryptions, in transit: SSL. It complies with HIPAA and HiTECH Act requirements. Only the participant, study team, outpatient MOUD providers, and necessary Q2i's personnel will have access to the OARSCM program and MyMAT application. OARSCM requires multi-factor authentication to create an account and access the program for both patients and providers. OARSCM and MyMAT can be accessed as a mobile application from a smart phone or tablet or through a computer with internet connection. If using a computer, OARSCM prompts users to close their browser when logging out. See "APPENDIX" for screenshot of prompt.

A HIPAA waiver of authorization has been obtained from the IRB in order to access medical records for to determine eligibility of potential subjects for the subject interviews. Additionally, patients will sign a HIPAA authorization during the consent process for interviews.

If the patient is excluded or refuses, this information, along with the reason for exclusion, will be documented on the Screening Log to allow comparisons of those enrolled vs. not enrolled, which will allow the team to assess representativeness of the sample

28. COMPENSATION FOR RESEARCH-RELATED INJURY

This research involves no more than minimal risk or harm to subjects. However, the subjects will be informed during the consent process of the following: "The University of Massachusetts Medical School does not provide funds for the treatment of research-related injury. If you are injured as a result of your participation in this study, treatment will be provided. You or your insurance carrier will be expected to pay the costs of this treatment. No additional financial compensation for injury or lost wages is available."

29. ECONOMIC BURDEN TO SUBJECTS

Participant smart phone data may be used to participate in the research. The participant would be responsible for any data charges to their phone plan during the course of participation. All insurance plans are accepted by the UMass Bridging Clinic, by CleanSlate, by SaVida Health, by Eleanor Health, and by Spectrum Health Systems. The cost of MOUD treatment is standard and covered by their insurance provider, copays will vary depending on patient's insurance provider.

Participation in this study will not cost patients any additional economic burden by going to the UMass Bridging Clinic, to CleanSlate, to SaVida Health, to Eleanor Health, or to Spectrum Health Systems compared to routine MAT treatment at any provider in the community. There will be no cost to the Acute Care or MAT clinicians to participate in the study.

30. CONSENT PROCESS

The consent process will be conducted in accordance with HRP-802 INVESTIGATOR GUIDANCE: Informed Consent.

Patients: The Patient consent process refers to subjects in all applicable aims. The RA(s) will approach each patient in his/her room after the patient has been medically assessed and stabilized by medical staff. They will explain the nature, purpose, risks, and benefits of the study. To assess for competency, a mini quiz will be administered to ensure that all potential subjects possess an understanding of the risks and benefits of study participation. The mini quiz consists of four multiple choice questions, which will be asked after the entire consent form has been thoroughly reviewed. Potential subjects will be given two attempts to answer all questions correctly; if a patient provides an incorrect answer, a research team member will review the corresponding section of the consent form and will give the patient another opportunity to answer the question. If a potential subject does not answer all four questions correctly after two attempts, the subject will not be enrolled in the study. The consent process will be conducted in-person; the research staff will verbally review the consent and HIPAA forms with the participant in REDCap. We will let the participant review an electronic copy of the consent upon request. The participant and the research staff will both electronically sign through REDCap's "Signature" feature. The participant will then choose whether they would like to receive an emailed PDF copy of the consent or a PDF paper copy of the consent sent to their address. Depending on which they choose, the REDCap survey will then branch to either enter the participant's email address or mailing address. The subject's email/home address will be deleted as soon as the consent form has been sent to the subject and are not being collected as part of the study design. See "HUMAN PARTICIPANTS PROTECTION" (p. 19) "Informed Consent" for additional details.

Clinicians (Phase 1): Waiver of written documentation of consent will be obtained for the clinician interviews. The research involves no more than minimal risk of harm to subjects and involves no procedures for which written documentation of consent is normally required outside of research context. Study procedures will be described verbally. An information sheet will be provided to the clinicians informing them about the study and that their participation is voluntary.

31. PROCESS TO DOCUMENT CONSENT IN WRITING

Patients: The consent process will be conducted in-person; the research staff will verbally review the consent and HIPAA forms with the participant in REDCap. We will let the participant review an electronic copy of the consent upon request. The participant and the research staff will both electronically sign through REDCap's "Signature" feature. The participant will then choose whether they would like to receive an emailed PDF copy of the consent or a PDF paper copy of the consent sent to their address. Depending on which they

choose, the REDCap survey will then branch to either enter the participant's email address or mailing address. The participant's email/home address will be deleted as soon as the consent form has been sent to the subject and are not being collected as part of the study design.

32. DRUGS OR DEVICES

Data generated from this study will be used to support a 510k submission to seek clearance as an FDA cleared device.

Statistical Design and Power

Data analyses will proceed with the intent-to-treat sample. Initial analyses will compare groups on baseline and demographic variables using chi-square test (for categorical variables) and analysis of variance (for continuous variables). Variables that significantly differ between groups or are theoretically important, such as pain and other (non-opioid) substance use disorder will be used as covariates in multivariate analysis, when appropriate. For end-of-treatment outcomes, analysis will compare groups via chi-square, Kruskal-Wallis test, and analysis of variance (ANOVA) or analysis of covariance (ANCOVA) tests, as appropriate. Evaluation of changes in outcomes through the follow-up period will occur with hierarchical mixed models specified for dichotomous or continuous outcomes (PROC MIXED and PROC GLIMMIX SAS procedures). These analyses allow for intra-subject serial correlation, unequal variance and covariance structures, and unequally spaced assessment intervals. They also account for missing data by using all available data and maximum likelihood estimation of parameters. To use the mixed effect modeling analysis in assessing intervention effect, an interaction term (intervention group by time) will be included together with other covariates (e.g., age, ethnicity, chronic pain, anxiety, trauma history, utilization of psychiatric or medical services). A significant beta coefficient of the interaction term at $p < .05$ level will be used as evidence supporting the intervention effect. Analysis of change scores can analyze variables that cannot be normalized. For all analyses, effect sizes will be estimated, with parametric and non-parametric statistics as appropriate; effect sizes for effects by sex will be estimated. Statistical significance will be at $p < .05$ and analyses will occur via IBM® SPSS® Statistics V21 and SAS 9.4 statistical software package (SAS Institute Inc, Cary, NC).

Phase 1, Usability Testing Stage. Analyses will center around assessing usability, acceptability, and needs for program updates based on users' experiences. We will apply descriptive statistics to assess participants' comments and questions related to specific program/equipment features and global assessments. Usability outcomes will be: 1) ability to use the program and equipment without staff assistance after training (yes/no), 2) time (in minutes) to complete the CM process once trained, and 3) total number of deviations from the direct path of completing CM procedures after training. Acceptability outcome will be an average SUS score of ≥ 80 .¹³² Pearson product moment and Spearman's rank correlations will examine relations between baseline characteristics (e.g., reading level) and usability and acceptability outcomes. A MySQL database administered through phpMyAdmin will track and store usage statistics, including time on each page, time in app, frequency and timing of pulling instructions. Google Analytics will constitute a secondary source of statistics.

Phase 1, Proof-of-concept usability field test Stage. Primary analyses will assess usability and acceptability, mirroring those above (Focus groups section). In addition, a MySQL database administered through phpMyAdmin will track and store usage statistics, including time on each page, time in app, frequency and timing of pulling instructions. Google Analytics will constitute a secondary source of statistics. SUS and program feature ratings will be examined with descriptive statistics.

Phase 2, RCT. will proceed with the intent-to-treat sample. Initial analyses will compare groups on baseline and demographic variables using chi-square test (for categorical variables) and analysis of variance (for continuous variables). Variables that significantly differ between groups or are theoretically important, such as pain and other (non-opioid) substance use disorder will be used as covariates in multivariate analysis, when appropriate. For end-of-treatment outcomes, analysis will compare groups via chi-square, Kruskal-Wallis test, and analysis of variance (ANOVA) or analysis of covariance (ANCOVA) tests, as appropriate. Evaluation of changes in outcomes through the follow-up period will occur with hierarchical mixed models specified for dichotomous or continuous outcomes. To use the mixed effect modeling analysis in assessing intervention effect, an interaction term (intervention group by time) will be included together with other covariates (e.g., age, ethnicity, chronic pain, anxiety, trauma history, utilization of psychiatric or medical services). A significant beta coefficient of the interaction term at $p < .05$ level will be used as evidence supporting the intervention effect. Analysis of change scores can analyze variables that cannot be normalized.

The Primary Aim 1 is to assess the efficacy of OARS+CM in promoting Suboxone treatment initiation.

The primary outcomes will be the proportion of participants who schedule a Suboxone treatment intake visit, and the proportion of participants who complete the Suboxone intake visit to start outpatient treatment. These outcomes are usually non-normally distributed and will be analyzed accordingly. We will assess the effect of the intervention using generalized linear mixed model, controlling for the dependence of repeated measures and the clustering effects.

Sample size justification. We use the proportion of participants who complete the Suboxone intake to start treatment as the calculating indicator. Based on the findings from a large randomized clinical trial on MAT treatment for opioid dependence after an acute care visit,¹⁵⁸ we estimate the proportion of patients who will initiate MAT at baseline is about 35%. We hypothesize that OARS will increase the rate by 25% and OARS+CM will increase the rate by 50%. Using G-Power program (proportions procedure) with $\alpha=0.05$, $N=150$ (50 each group), the calculated statistical power is >0.80 for the comparisons between TAU and OARS, TAU and OARS+CM, and OARS and OARS+CM.

Aim 2 is to assess the efficacy of OARS+CM for increasing Suboxone treatment adherence and abstinence outcomes. Main outcomes will be the percentage of opioid-free urine toxicology tests, and the percentage of group/individual therapy sessions attended. Secondary outcomes will be the longest duration of abstinence (LDA) outcome, measured at month 1, month 3 (end of study period) and month 6 (end of follow-up period), and sustained abstinence from Suboxone start through each follow-up. LDA and sustained abstinence will be as a composite of the greatest number of days with consecutive negative urine samples and self-reported no use; a composite of biochemical evidence and subjective report is needed because urine tests are too infrequent in the clinical setting to rigorously determine sustained abstinence based solely on biochemical evidence. Sustained abstinence and LDA are usually non-normally distributed and will be examined accordingly. We will assess the effect of the intervention using linear mixed model, controlling for the dependence of repeated measures and the clustering effects.

Aim 3 is to evaluate costs. Economic evaluation of the CM intervention is highly relevant to considerations of implementation and will be informed by expert guidelines.¹⁵⁹ The primary hypothesis is that the incremental cost-effectiveness (cost per participant who does not have repeat OUD-related emergency acute care, measured at the end of treatment and the last follow-up) will be acceptable and support sustainability. The study will also determine the incremental cost of the CM intervention per OUD patient treated, to identify the budget impact of adoption on a large-scale basis if the intervention is efficacious. For analyses, we will determine the Incremental Cost Effectiveness Ratio (ICER) in dollars per repeat acute care visit averted. This ratio is the difference in cost incurred by the OARS+CM group divided by the difference in the proportion of participants without repeat acute care services over the short (intervention period) and long term (last follow-up). The statistical uncertainty of the incremental cost-effectiveness will be estimated by bootstrap analysis of trial data, a method that preserves the covariance between costs and outcomes.¹⁶⁰ A cost-effectiveness acceptability curve will be plotted with the proportion of replicates that are cost-effective at different threshold values of willingness to pay per successful quit participant.¹⁶¹ The p -value for the statistical test that the OARS+CM intervention is cost-effective will be found by determining the proportion of replicates that are above each threshold value. We will conduct a literature review of cost-effectiveness studies to identify likely threshold values of dollars per OUD person treated in general. Costs of activities that are solely for research purposes (weekly surveys, follow-ups) will be excluded. Also see the Commercialization Plan for our approach to cost-savings and cost-avoidance.

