5. BACKGROUND*

See grant: "RESEARCH STRATEGY" (p.2-4) for details. The Procedures for Phase 2 have been modified from the original submission. Updated Procedures are as follows:

Procedures

Screening, recruitment, eligibility and training procedures are in C.2.1 and the Eligibility criteria document.

Randomization will occur following determination of eligibility using an urn procedure and stratifying on 1) other (than opioid) substance use disorder no/yes, 2) gender/sex, 3) race/ethnicity.

TAU with MyMAT (n = 51). In the acute care setting, the Behavioral Health Service run by Drs. [name] and [name] provides SBIRT for substance use disorders, including OUD. They provide SBIRT as part of TAU, including, when possible, warm handoff contact with outpatient MOUD treatment that includes a scheduled outpatient appointment, optimally within 48 hours of the ED visit. Patients randomized to this group will also receive MyMAT, a mobile application with opioid treatment educational content, as an attention control measure against OARS+CM. TAU outpatient suboxone treatment consists of urine toxicology screening, group/individual therapy, and MOUD prescription continent on drugnegative (except cannabis, which is legal in MA) urine toxicology. Treatment visits are typically, weekly in weeks 1-4 and then taper over time, to every other week in weeks 5-8, and monthly in weeks 9-12 and thereafter. Nonadherence can lead to increased frequency/intensity of therapy and urine toxicology until the patient stabilizes. If increased frequency/intensity is unsuccessful, patients may be referred to detoxification and subsequently re-admitted to outpatient care when appropriate.

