5. Patient will not receive any follow up calls after the hospital visit but will have their use of the OARSCM mobile application and engagement with treatment as tracked by the OARSCM mobile application monitored for 4 weeks. Participation in this study will last about 4 weeks once the patient has started MAT treatment. After these 4 weeks, the participants will be informed that their 4-week participation has now ended and that we appreciate their participation. They will also be informed that new information related to their appointments, appointment attendance, appointment engagement and tox results will not be entered into their OARSCM mobile application profile. However, they will be able to view this DATA that had been previously entered throughout the 4-weeks. They will continue to have access to their OARSCM mobile application account in order to use their unredeemed Spins, Prizes, and eGift cards for a short time. During enrollment, patient participants will be given a handout on how to uninstall the application if they no longer want the application on their smart phone after participation. See grant: "RESEARCH STRATEGY" (p. 8). See grant: "APPENDIX" for screenshot of patient notification that their 4-week participation has now ended and handout of how to uninstall the mobile application.

Phase 2: Aims 1 and 2 (Efficacy of OARSCM): 102 patients randomized to 1 of 2 groups If the patient agrees to participate:

- 1. Participants (acute care patients who meet eligibility criteria and complete consent process, see section 30. Consent Process) will be randomized to either TAU (with MyMAT) or OARS mobile application plus contingency management (OARSCM).
- 2. Participants will complete an interview assessment during their current medical visit. It takes about 20-30 minutes to complete. They will be asked to provide a urine sample. It will not interfere with their care.
- 3. Participants will be provided a warm handoff to a community-based MOUD treatment provider. All participants will be eligible to receive standard MOUD treatment per treatment as usual at the site they are referred to. If they are randomized to OARSCM, they will use the mobile application to track treatment progress and have the potential to earn prizes for engaging with the application throughout treatment.

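### The SAP lets baseline significance tests and open wording choose the covariates instead of fixing the three randomisation factors; the cost is minor and the fix is short

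*SAP*

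**What the plan says.** Protocol section 5 (Background, Procedures) randomises by urn, "stratifying on 1) other (than opioid) substance use disorder no/yes, 2) gender/sex, 3) race/ethnicity". Section 6 sets N=102, allocated 1:1, so 51 per arm.

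The SAP's opening section (Statistical Design and Power) and its Phase 2 RCT paragraph both begin with chi-square and ANOVA comparisons of the groups at baseline. Both then state that "Variables that significantly differ between groups or are theoretically important, such as pain and other (non-opioid) substance use disorder will be used as covariates", and both soften this with a clause leaving it to judgement.

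For the mixed models over follow-up, the group-by-time term is entered "together with other covariates (e.g., age, ethnicity, chronic pain, anxiety, trauma history" and a few more), as an open list of examples. The opening section's only commitment on sex is that "effect sizes for effects by sex will be estimated".

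The two primary outcomes are scheduling and completing a Suboxone intake. The Phase 2 RCT paragraph analyses them with a "generalized linear mixed model, controlling for the dependence of repeated measures and the clustering effects" and names no baseline covariate. The sample size paragraph assumes 35% intake completion under usual care, states that "OARS+CM will increase the rate by 50" percent, and reports power above 0.80 with 50 per group.

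**The concern.** A trial that balances on certain factors should normally adjust for them: leaving prognostic balancing factors out makes the test conservative. Here the only data-based route into the model is a significant baseline difference. Under proper randomisation such a difference is chance by definition and says nothing about whether the variable predicts outcome. The urn also makes its own factors the least likely to show one. The other route, theoretical importance, is open-ended.

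Several covariate sets therefore fit the text for the same primary comparison, and a borderline p-value could fall on either side of .05 depending on which is used. That should be settled in advance in a trial of which the protocol says (section 32): "Data generated from this study will be used to support a 510k submission".

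**Working it through.** **1. The three factors against the SAP.**

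| Urn factor | Treatment in the SAP |
|---|---|
| Other SUD | Named as an example of an important covariate, subject to judgement |
| Race/ethnicity | Ethnicity only, in the illustrative list for the group-by-time models |
| Gender/sex | Effect sizes by sex; not named as a covariate |

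**2. The plan's power figure.** The 50% increase can mean percentage points (35% v 85%) or a relative rise (35% × 1.5 = 52.5%). Pooled normal approximation, two-sided 5%:

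power = Φ{[|p2−p1|√n − 1.96√(2p̄(1−p̄))] / √[p1(1−p1)+p2(1−p2)]}

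- At the plan's n=50: 35% v 85% gives 0.9999; 35% v 52.5% gives 0.42 (one-sided 0.55). Only the percentage-point reading matches the stated power for the comparison that remains in the two-arm design.
- At n=51, 35% v 85%: (3.571 − 1.358)/0.5958 = 3.714, power 0.9999.
- At n=51, 35% v 52.5%: (1.250 − 1.375)/0.6906 = −0.181, power 0.428.
- At n=51, 35% v 63% (not in the plan; chosen as a case near 80%): power 0.817.

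**3. What the significance rule selects.** The chance that at least one of k independent baseline tests is significant is 1 − 0.95^k: 22.6% for k=5, 33.7% for k=8, 40.1% for k=10. In simulated urn randomisation (20,000 trials per urn type, 1 to 5 starting balls per arm), sex and race/ethnicity each reached p<.05 in 0.2–0.9% of trials, against about 5% without balancing. At least one of four irrelevant variables did so in 18–19% (1 − 0.95^4 = 18.5%).

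**4. Size and power.** Assumptions, none from the documents: factor prevalences 0.5, 0.4 and 0.35; odds ratio (OR) 1.5 to 3 per factor; pain OR 1.5 per SD; four irrelevant variables; one binary outcome per person; logistic Wald test. The SAP-like rule puts other SUD and pain in, and the rest only if significant at baseline. The fixed model has the three factors plus pain. There were 60,000 null trials and 20,000 per alternative. For power, each test is held to its own simulated 5% critical value. Ranges cover two urn types.

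| OR per factor | Type I error, SAP-like rule | Type I error, fixed | Power gain, 35% v 52.5% | Power gain, 35% v 63% |
|---|---|---|---|---|
| 1.5 | 4.75–4.98% | 5.12–5.35% | −0.13 to 0.54 points | 0.25–0.34 |
| 2 | 4.74–4.77% | 5.17–5.22% | 0.66–1.11 | 0.75–0.78 |
| 3 | 4.30–4.45% | 5.15–5.24% | 1.59–1.98 | 1.67–1.76 |

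Monte Carlo SE is about 0.3 points. At 35% v 85% the gain is −0.03 to 0.01.

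A further simulation forced no covariate in and compared the tests at nominal 5%. With log-odds 0.5, 1.0 and 1.5 per factor (ORs 1.65, 2.72, 4.48), power at 35% v 60% was 0.69, 0.58 and 0.44 for test-picked covariates, and 0.71, 0.63 and 0.53 with the three factors fixed. These gaps overstate the SAP's loss, because the SAP names other SUD and pain and because the tests differ in size.

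**5. How often the p<.05 verdict depends on the set.** Four permitted sets were compared: other SUD and pain always in, sex and race/ethnicity each in or out.

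| True rates | Main simulation | Second run | Third run |
|---|---|---|---|
| No effect | 1.5–3.3% | 1.2–2.6% | 1–2% |
| 35% v 52.5% | 5.0–11.6% | 4.1–9.9% | about 3–7% |
| 35% v 63% | 3.2–6.2% | 3.2–6.3% | – |
| 35% v 85% | at most 0.05% | at most 0.07% | essentially none |

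The text also permits an unadjusted test, which is not among the four.

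**6. Group-by-time term.** Baseline main effects are constant within a person and drop out of within-person change. In a random-intercept linear model (visits at 1, 3 and 6 months; 40 simulated trials per setting), adding sex and race/ethnicity changed the interaction's SE by a ratio of 1.0000 with complete data and 0.9975 with 25% of visits missing. The group coefficient's SE fell 3–4%.

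**7. The scheduling outcome.** The warm handoff offers appointment scheduling to both arms, so this rate may be high; the documents give no figure. If 95% schedule, 102 × 0.05 = 5.1 people do not, against five slope coefficients (group, three factors, pain). Ordinary logistic regression had no finite fit in about 8–11% of simulated trials at an assumed 90% and 40–45% at 95%. With only other SUD and pain the figures were about 1.5% and 17–19%. At 80% the full set failed in under 1%.

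**The case against.** The strongest reply is that almost nothing is lost. The gain is within simulation noise at OR 1.5 and about 1 point at OR 2. Only the 35% v 85% reading fits the plan's stated power, and there the gain and the disagreement between sets both vanish. The disagreement at 35% v 52.5% partly reflects that any two valid models disagree more often when power is about 43%; it is not an error rate. The gap is also narrower than three missing factors: other SUD is named, ethnicity is listed, and gender/sex is the clear omission. All of this stands and sets the size of the point. It does not supply a closed covariate list or justify selection by baseline test.

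A caution about the remedy also stands: three factors plus pain can break ordinary logistic regression for the scheduling outcome.

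Three stronger readings are tempting and not supported:

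- A reader might infer that the significance rule inflates type I error. It does not; simulated size is 4.3–5.0%.
- A reader might infer that the set would be chosen after seeing results. If so, type I error would reach 5.8–6.5% at most across the four sets, but nothing in the documents says this would happen.
- A reader might extend the point to the group-by-time test. Step 6 shows that test is virtually unaffected.

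**Conclusion.** The gap is real and minor. The SAP states a selection rule that tracks chance, does not commit to the factors used in randomisation, and leaves the primary covariate set open. The consequences are slightly conservative tests, about 1 point of power (up to 2 at OR 3), and a verdict that depends on the chosen set in roughly 3–12% of trials if the true rates are near 35% v 52.5%. At 35% v 85% there is essentially no consequence.

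These sizes rest on assumed prognostic strength, prevalences and urn settings, and on a single-outcome logistic model standing in for the planned mixed model. The textual finding does not depend on them. The case for change is that it costs very little.

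**What to change.** 1. For intake completion and the group comparisons on the Aim 2 main outcomes (opioid-free urine tests, therapy sessions attended), adjust for other SUD, gender/sex, race/ethnicity collapsed to categories listed in advance, and pain. State this as a closed list, without the clause leaving it to judgement, and name the pain score.
2. In both SAP paragraphs, delete the rule that variables differing significantly at baseline become covariates. Keep the baseline comparison as description.
3. Use the same list for the scheduling outcome only with a stated sparse-data method, such as Firth-penalised logistic regression or a named reduced set if events or non-events are few.

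The illustrative covariate list for the group-by-time models can stay as far as this point goes.

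Cost: a few SAP sentences and no new data. The downsides are lost race/ethnicity detail from collapsing, a few extra parameters at N=102, and a fixed model that ran slightly above nominal size in simulation (5.1–5.4%).
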